# **Study Protocol**

## **Development of Pneumonia Due to Alveolar Glucose Levels in Systemic Hyperglycemia**

Version: 2  
Date: 08/01/2017

1. General study design:

Monocentric prospective clinical observational study

2. Schedule:

Inclusion of the first patient: 08/01/2017

Inclusion last patient: 12/31/2018

Close the database: 01/31/2019

End of the statistical evaluation: 06/31/2019

3. Study endpoint, duration of study:

The primary endpoint of the study is the incidence of pneumonia

4. Sample size calculation:

The sample size estimate was based on the assumption that in the investigated patient population the occurrence of pneumonia could be expected in 10% of the patients. Thus, for an unconnected sample, a ratio (m) of 0.9 controls per incidence of pneumonia. In a previous study (Bacterial respiratory tract infections are promoted by systemic hyperglycemia after severe burn injury in pediatric patients, Kraft et al., Burns, 2014, May), it was found that the mean values ( $\delta$ ) of both groups for glucose differed by about 30 mg / dL in the mean with a standard deviation ( $\sigma$ ) of 20 mg / dL. Under the same conditions, 14 controls and 16 patients with pneumonia are needed to reject the null hypothesis with a probability (power) of 0.9.

The occurrence of the first type error ( $\alpha$ ) was set at 0.01. Design: Independent  $\alpha = 0.01$ ; power = 0.9;  $\delta = 30$ ;  $\sigma = 20$ ;  $m = 0.9$ ;  $n = 16$ ;

t-test confidence interval width = 40.68604

Calculated with PS Power and SampleSize Calculator Version 3.0,

<http://biostat.mc.vanderbilt.edu/PowerSampleSize>

5. Selection of the study population:

Patients undergoing elective cardiac surgery matching inclusion and exclusion criteria

6. Subsequent exclusion of study patients:

Reasons for a subsequent exclusion of the patient only apply if subsequently it is determined that not all inclusion criteria are met or exclusion criteria that were not initially recognized. These patients are also excluded from the documentation.

7. Documentation / Evaluation:

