All study-relevant data are recorded in the provided documentation sheets by the responsible study physicians and, if necessary, the study assistants. The study forms are digitized and stored in the in-house EDP system in compliance with the safety guidelines using the programs Microsoft Excel® and Access®. Radiological images are stored in digital form, preferably in TIFF or raw data format. The statistical analysis is carried out by means of the programs Sigmastat® and SigmaPlot®.

The statistical evaluation is carried out on the one hand with regard to the cut-off value of the glucose threshold of the lung by means of Receiver Operating Characteristic (ROC). This is used to validate our findings in comparison to the already existing preliminary studies. The evaluation of dichotomous variables is performed by Chi Square Test or, if necessary, by Logistic Regression Analysis.

Constant features are compared using Student's t-test, analysis of variance between the groups. With regard to the presence of disturbing variables between the two groups, the formation of subgroups, possibly a matching by means of a propensity score, is planned.

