#### 8. Study plan:

Timepoint 1, preoperative:

Obtaining informed consent and inclusion in the study, blood draw  
Preoperative chest X-ray (clinical routine)

Timepoint 2, Operative Intervention:

Blood draw, asservation of alveolar secretions (endobronchial after intubation)

Timepoints 3.1 – 3.n, postoperative (daily):

Blood draw, asservation of alveolar secretions (if ventilated) chest X-ray (if clinically needed)

Timepoint 4, Discharge:

Final evaluation

Patients will be included in the study, if fulfilling the inclusion criteria and missing exclusion criteria. Written informed consent will be obtained from the patients.

Patients will be pseudonymised by assigning a sequential number.

Anonymization of the patients cannot be considered in such a conceived study, since the change of personal data makes an assignment of essential clinical course data impossible.

Blood draws:

Blood will be collected by puncture or draw by venous or arterial catheter during the clinical routine for determination of leucocyte count, CRP value, and blood sugar. Blood samples will be analyzed in the in-house laboratory. Blood sugar levels are additionally measured in the intensive care unit using a blood gas analyzer.

In addition, one blood sample EDTA and one serum are collected (9 mL each). The centrifugation and aliquoting of the obtained plasma and serum samples will be spinned down and aliquoted. The samples are stored at -80 ° C in the laboratory rooms of the Cardiac Surgery Department for later analysis.

X-ray:

The evaluation of the radiological images of the chest is carried out as part of the clinical requirements. There is no additional requirements of radiological examinations due to the study.

Endobronchial sampling:

The endobronchial sampling of alveolar fluid will be performed by utilizing the inserted tube and aspiration with a suction catheter. Two samples are taken. The first sample is sent to the in-house laboratory immediately after sampling for microbiological analysis. The second sample is stored at -80 ° C in the premises of the cardiosurgical research department until later analysis.

Clinical evaluation/examination:

There is a daily clinical examination of the patients for signs of pneumonia.

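### The lung-glucose ROC is called validation, yet no earlier cut-off is stated and its marker, outcome and sample are undefined; a cut-off chosen and assessed in this cohort would look too accurate on average

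*Protocol*

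**What the plan says.** Protocol section 7 (Documentation / Evaluation) sets out an evaluation of the "cut-off value of the glucose threshold of the lung by means of Receiver Operating Characteristic (ROC", and continues: "This is used to validate our findings in comparison to the already existing preliminary studies". The SAP, under Documentation / Evaluation, repeats both statements.

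Neither document gives a numerical cut-off from earlier work, a rule for choosing a new one, or an interval for the cut-off or its accuracy. The only earlier study named is the one in paediatric burn patients. It is cited in section 4 for the sample size, and no cut-off is quoted from it.

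Section 8 does provide for alveolar samples. At operation it lists "Blood draw, asservation of alveolar secretions (endobronchial after intubation", and on each postoperative day "Blood draw, asservation of alveolar secretions (if ventilated) chest X-ray (if clinically needed". The number of samples per patient therefore depends on ventilation time. Nothing links a particular sample or summary to the ROC. Section 8 specifies blood sugar measurement, but names no glucose assay for the stored alveolar sample.

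**The concern.** Validating a threshold means fixing a number in advance and testing it in new patients. Finding a threshold by ROC is derivation. The plan uses the word for the first without supplying the number that the first requires.

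The difference matters because a cut-off that maximises accuracy in a small cohort fits that cohort's chance variation. Its sensitivity and specificity in the same patients are then better, on average, than they would be in new ones. The ROC is neither the primary endpoint nor the basis of the sample size. It is, however, the only planned analysis tied specifically to lung glucose and the only one described as validation. A derived cut-off reported under that word would be taken as stronger evidence than it is.

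The undefined marker, outcome and sample add to this. Without them, a reader cannot tell what the ROC discriminates, or whether the value used came before the pneumonia.

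**Working it through.** **Inputs.** From Protocol section 4 (repeated in the SAP): difference 30 mg/dL, SD 20 mg/dL, α = 0.01, power 0.9, m = 0.9 controls per case, 16 cases and 14 controls, expected pneumonia incidence 10%. There is no size or precision target for the ROC.

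**The plan's own figure.** For a two-sided two-sample t-test, n = (t₀.₉₉₅ + t₀.₉₀)² × σ² × (1 + 1/m) / δ², iterated on the degrees of freedom. Here σ²/δ² = 400/900 = 0.444 and 1 + 1/0.9 = 2.111. This converges to 15.61 cases and 0.9 × 15.61 = 14.05 controls, i.e. 16 and 14. The confidence interval width at the unrounded n is 40.686, as stated, and power at 16/14 is 0.899. The figure reproduces, but it sizes a comparison of mean glucose, not a ROC.

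**Two cohort sizes.** One is 16/14 as stated. The other follows from the 10% incidence: 16/0.10 = 160 patients, and 160 − 16 = 144 without pneumonia.

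**Simulation.** The following are assumptions that are not in the documents: normal values with equal SD, one value per patient, pneumonia as the outcome, the 30/20 mg/dL figures carried over to the ROC marker, and a cut-off that maximises J = sensitivity + specificity − 1 (Youden). There were 20,000 cohorts per setting, with the cut-off midway between observed values. Apparent J is computed in the same cohort; true J is the accuracy of that cut-off in the population.

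| Difference/SD | Cases/non-cases | Apparent J | True J | Excess |
|---|---|---|---|---|
| 1.5 (30/20) | 16/14 | 0.655 | 0.510 | 0.145 |
| 1.5 (30/20) | 16/144 | 0.626 | 0.520 | 0.106 |
| 0.75 | 16/14 | 0.434 | 0.257 | 0.177 |
| 0.75 | 16/144 | 0.396 | 0.266 | 0.130 |
| 0 | 16/14 | 0.200 | 0.000 | 0.200 |
| 0 | 16/144 | 0.153 | 0.000 | 0.153 |

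At 30/20 with 16/14, mean apparent sensitivity and specificity are 0.815 and 0.840, against true values of 0.748 and 0.763. With 16/144 they are 0.839 and 0.787, against 0.743 and 0.777, so nearly all the excess is in sensitivity. Apparent J exceeds true J in about 87% of cohorts at either size.

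**Stability of the chosen cut-off.** At 30/20 its central 95% range is about 33 mg/dL wide (16/14) or 28 mg/dL wide (16/144). That is about as wide as the 30 mg/dL group difference itself, so agreement with an earlier value means little without an interval.

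**AUC.** The true value is Φ(1.5/√2) = 0.856. The simulated mean is 0.856 (16/14) and 0.855 (16/144), and about 0.50 with no association. Choosing a cut-off does not inflate the AUC of one prespecified marker.

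**Bootstrap correction.** Share of optimism removed = (apparent − corrected)/(apparent − true), from 800 cohorts with 200 resamples each.
- 30/20, 16/14: (0.652 − 0.563)/(0.652 − 0.507) = 0.61.
- 30/20, 16/144: (0.624 − 0.558)/(0.624 − 0.518) = 0.62.
- No association: (0.196 − 0.076)/0.196 = 0.61 (16/14) and (0.158 − 0.066)/0.158 = 0.58 (16/144).

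Repeat runs put the share at roughly 60 to 70%. A nominal 95% bootstrap interval for the cut-off covered 94% at 16/14 but only 87% at 16/144.

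**If an earlier cut-off is applied unchanged.** There is no selection bias, only imprecision. Exact 95% intervals for example counts are 0.48–0.93 for 12/16 cases, 0.49–0.95 for 11/14 controls and 0.67–0.82 for 108/144 non-cases.

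**The case against.** The strongest reply is that the documents never say a cut-off will be derived and then credited with its own in-sample accuracy. The preliminary studies may contain a number that would be applied as it stands. The sentence also speaks of checking this study's findings against earlier ones, which could mean no more than comparing two thresholds, and no report of sensitivity or specificity is promised. This stands: the overstatement is conditional on derivation and on reporting accuracy in the same patients. It does not rescue the word validation, because the plan contains no number to validate.

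A second reply is that the marker may not be alveolar glucose at all. The wording could mean the blood glucose level above which glucose appears in the lung, with the alveolar value as the outcome. This also stands. On that reading the group sizes above would not apply directly, so the marker and outcome have to be stated first.

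Three stronger inferences are tempting but unsupported:
- That the plan names no alveolar sample. Section 8 lists them; only the link to the ROC is missing.
- That the accuracy will certainly be inflated. A cut-off fixed beforehand has no selection bias.
- That the AUC is inflated as well. Cut-off selection does not do this, and nothing in the plan says that the sample will be picked after seeing results or that a per-patient maximum will be used.

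**Conclusion.** The point holds in conditional form. The plan calls the ROC validation without an earlier cut-off, and does not define its marker, outcome or sample. If the cut-off is chosen here and its accuracy reported in the same patients, sensitivity + specificity − 1 is overstated by about 0.15 (16/14) or 0.11 (16/144) at the plan's own effect size, and by 0.20 or 0.15 with no association. These sizes rest on the Youden rule, normal values and the carry-over of 30/20 mg/dL to the ROC marker; section 4 does not say whether that glucose figure is from blood or lung. The overstatement appeared in every setting examined, but its size varies. This is a cheap improvement worth making for a secondary analysis. It is not a defect in the primary endpoint or the sample size.

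**What to change.** Amend the SAP before analysis.

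1. If the preliminary studies supply a numerical cut-off, state it and its source, apply it unchanged, and report sensitivity and specificity with exact 95% confidence intervals. Call only this validation.
2. Otherwise label the cut-off exploratory and state its selection rule. Report bootstrap optimism-corrected sensitivity and specificity beside the apparent values, noting that the correction is partial (roughly 60 to 70% of the optimism in simulation). Describe any bootstrap interval for the cut-off as possibly under-covering.
3. On either route, state the ROC marker (alveolar or blood glucose), the outcome, and one value per patient taken before pneumonia is diagnosed. Report the AUC with a 95% confidence interval. If the marker is alveolar, the post-intubation sample is scheduled for every patient and does not depend on ventilation time. It precedes postoperative exposure, however, so the choice needs a justification. A per-patient maximum depends on how many samples were taken.

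The cost is SAP text and at most one bootstrap run, with no extra patients or samples. If the named software cannot run the bootstrap, another program must be named. The reported accuracy will be less favourable and the intervals wide, mainly for sensitivity.

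### Student's pooled-variance t-test is the only two-group test named for continuous variables; at the roughly 1:9 split implied by 10% incidence, it holds the 1% level only if both groups have the same SD

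*Protocol*

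**What the plan says.** Protocol section 7 (Documentation / Evaluation) gives the rule for continuous variables: "Constant features are compared using Student's t-test, analysis of variance between the groups". The SAP repeats the sentence under the same heading. Neither document names an unequal-variance test, a check of the variances or a rank test.

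The sentence does not mention glucose. Protocol section 4 and the SAP, however, base the sample size on a t-test of glucose. The groups are said to have "differed by about 30 mg / dL in the mean", with one SD of 20 mg/dL. The type I error "was set at 0.01", and the aim is to "reject the null hypothesis with a probability (power) of 0.9". The stated result is 16 patients with pneumonia and 14 controls.

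On group sizes, the same paragraph assumes that "the occurrence of pneumonia could be expected in 10% of the patients" and derives from this "a ratio (m) of 0.9 controls per incidence of pneumonia". Protocol section 1 describes a single-centre prospective observational study. No sampling of controls to a fixed ratio is described. Propensity matching is mentioned only as a possibility, to deal with confounding.

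**The concern.** Student's test estimates one common variance from both groups. When the groups are about the same size, it tolerates unequal SDs well. When one group is nine times the other, the pooled variance is almost entirely that of the large group, while the uncertainty of the difference comes mostly from the small group. If the pneumonia group has a different spread, the standard error is wrong. It is too small if cases vary more and too large if they vary less.

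Analysis of variance gives no protection: with two groups it is the same pooled test (F = t²).

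At stake is the 1% error rate that the plan chose for its sample-size comparison. The named test delivers that rate only under a condition that the documents neither support with group-specific figures nor plan to check.

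**Working it through.** **Inputs from Protocol section 4 and the SAP:** alpha 0.01, power 0.9, difference 30 mg/dL, SD 20 mg/dL, ratio 0.9, incidence 10%.

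**Assumptions:** normal data, control SD 20, and case/control SD ratio r from 0.67 to 2. A two-sided test is inferred, because the documents do not state sidedness.

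**1. The plan's own figure.** Noncentral-t power of the two-sided pooled test is 87.9% for 15 cases with 13.5 controls, 90.5% for 16 with 14.4, and 89.9% for 16 with 14. So n = 16 is reproduced. A one-sided test would need only 14 cases (90.7% with 12.6 controls), which is why two-sided is inferred. The 99% interval width at 16 vs 14 is 2 × 2.763 × 20 × √(1/16 + 1/14) = 40.45. The plan has "t-test confidence interval width = 40.68604", a difference of 0.6% that does not affect this point.

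**2. The split implied by the incidence.** 10% with pneumonia and 90% without gives 0.9/0.1 = 9 controls per case. Sixteen cases then mean 16/0.10 = 160 patients, that is 16 vs 144.

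**3. Why the split matters.** Compare the variance that Student's test uses on average with the true variance of the difference:

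- used: 400 × [(n₁−1)r² + (n₂−1)]/(n₁+n₂−2) × (1/n₁ + 1/n₂)
- true: 400 × (r²/n₁ + 1/n₂)

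At 16 vs 144 with r = 1.5:

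- used: 400 × (15 × 2.25 + 143)/158 × (1/16 + 1/144) = 31.1, so SE 5.57
- true: 400 × (2.25/16 + 1/144) = 59.0, so SE 7.68

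The critical value 2.607 therefore acts like 2.607 × 5.57/7.68 = 1.89. The normal two-sided tail beyond 1.89 is about 5.9%.

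At 16 vs 14 with r = 1.5 the two SEs are 9.46 and 9.21, almost the same.

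**4. Type I error by simulation** (4 million draws per row, nominal two-sided 1%):

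| r | Student, 16 vs 144 | Welch, 16 vs 144 | Student, 16 vs 14 |
|---|---|---|---|
| 0.67 | 0.05% | 1.1% | 1.25% |
| 1.0 | 1.0% | 1.0% | 1.0% |
| 1.25 | 3.1% | 1.0% | 0.9% |
| 1.5 | 6.1% | 1.0% | 0.9% |
| 2.0 | 12.7% | 1.0% | 0.9% |

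More patients at the same split do not help Student's test. At r = 1.5 its error is about 6% at 3 vs 27, 8 vs 72 and 16 vs 144 alike.

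**5. Power for a 30 mg/dL difference:**

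| Design | r | Student | Welch |
|---|---|---|---|
| 16 vs 14 | 1.0 | 89.9% | 89.6% |
| 16 vs 144 | 1.0 | 99.9% | 99.5% |
| 16 vs 144 | 1.25 | 99% | 94% |
| 16 vs 144 | 1.5 | 98% | 82% |
| 16 vs 144 | 2.0 | 92% | 53% |
| 8 vs 72 | 1.0 | 91% | 74% |
| 3 vs 27 | 1.0 | 40% | 20% |

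Student's figures for r above 1 are bought with the inflated error in step 4.

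**The case against.** The strongest reply is that the plan states 16 vs 14. There Student's error stays between about 0.9% and 1.25% for these SD ratios (1.5% at r = 0.5). The 144 controls are an inference that overrides the plan's own ratio. This stands as a limit: the problem exists only if the split is near 1:9. But 0.9 controls per case does not follow from 10% incidence, and an unselected cohort would give nine. The conflict between the two ratios is the more basic fault.

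A second reply is that the harm needs unequal SDs, and the documents give only one SD. This also stands. A reader might infer that the study will have an inflated error rate. The documents do not support that: they say nothing on which group varies more, and the error could equally fall well below 1%.

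A reader might also take this for a fault in the primary analysis. It is not: Protocol section 3 names the incidence of pneumonia as the primary endpoint. The only analysis explicitly tied to a glucose level is the ROC cut-off, which this point does not touch. Glucose is the sample-size comparison and no more than that.

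Third, Welch's test has limits of its own:

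- **Few cases.** If 10% incidence is applied to 30 patients in total (3 vs 27), Welch's error is about 3%, and at equal SDs it does worse than Student's test.
- **Skewed data.** If both groups share one lognormal distribution at 16 vs 144, Welch's error is about 1.4% at a log-SD of 0.25 and 3.3% at 0.7, against 1.0% and 1.3% for Student's test.

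These limits stand, and they set the conditions on the fix.

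**Conclusion.** The point holds as a cheap improvement, not as a demonstrated error in the plan. Both documents name only pooled-variance methods. At the 1:9 split that the incidence and the cohort design imply, the 1% level then depends on equal SDs: an SD 25% larger among cases triples the error to about 3.1%, and an SD one third smaller cuts it to about 0.05%.

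The conclusion rests on four conditions: a split near 1:9, roughly 16 cases, approximately normal data, and an SD ratio that is assumed rather than documented.

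**What to change.** In Protocol section 7 and the SAP, replace Student's t-test with *Welch's unequal-variance t-test* for two-group comparisons of continuous variables, including glucose. Report Student's test as a sensitivity analysis. State the sidedness. Specify that a markedly skewed variable is log-transformed before testing.

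Separately, reconcile the 10% incidence with the ratio of 0.9 controls per case, and state the total number of patients that 16 cases require (about 160 if the 10% is kept and controls are not sampled).

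The cost of the test change is a line of wording in each document. If the SDs are equal, it gives up 0.4 percentage points of power at 16 vs 144 and 0.3 at 16 vs 14. If cases vary more, the sponsor should know that power at 16 vs 144 falls below the planned 0.9 somewhere between SD ratios of 1.25 (94%) and 1.5 (82%). If far fewer than 16 cases accrue, the choice of test should be revisited before glucose is compared between the groups, since Welch's test then loses much of its power and, at about three cases, its own error control.

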#### 8. Study plan:

Timepoint 1, preoperative:

Obtaining informed consent and inclusion in the study, blood draw  
Preoperative chest X-ray (clinical routine)

Timepoint 2, Operative Intervention:

Blood draw, asservation of alveolar secretions (endobronchial after intubation)

Timepoints 3.1 – 3.n, postoperative (daily):

Blood draw, asservation of alveolar secretions (if ventilated) chest X-ray (if clinically needed)

Timepoint 4, Discharge:

Final evaluation

Patients will be included in the study, if fulfilling the inclusion criteria and missing exclusion criteria. Written informed consent will be obtained from the patients.

Patients will be pseudonymised by assigning a sequential number.

Anonymization of the patients cannot be considered in such a conceived study, since the change of personal data makes an assignment of essential clinical course data impossible.

Blood draws:

Blood will be collected by puncture or draw by venous or arterial catheter during the clinical routine for determination of leucocyte count, CRP value, and blood sugar. Blood samples will be analyzed in the in-house laboratory. Blood sugar levels are additionally measured in the intensive care unit using a blood gas analyzer.

In addition, one blood sample EDTA and one serum are collected (9 mL each). The centrifugation and aliquoting of the obtained plasma and serum samples will be spinned down and aliquoted. The samples are stored at -80 ° C in the laboratory rooms of the Cardiac Surgery Department for later analysis.

X-ray:

The evaluation of the radiological images of the chest is carried out as part of the clinical requirements. There is no additional requirements of radiological examinations due to the study.

Endobronchial sampling:

The endobronchial sampling of alveolar fluid will be performed by utilizing the inserted tube and aspiration with a suction catheter. Two samples are taken. The first sample is sent to the in-house laboratory immediately after sampling for microbiological analysis. The second sample is stored at -80 ° C in the premises of the cardiosurgical research department until later analysis.

Clinical evaluation/examination:

There is a daily clinical examination of the patients for signs of pneumonia.
